6.1 DESCRIPTION OF PROCEDURES

Informed Consent

Screening

The subject must read, understand and sign the IRB-approved informed consent form (ICF) confirming his or her willingness to participate in this study before initiating any screening activity that is not standard of care. Subjects must also grant permission to use protected health information.

Medical History

Screening

Medical history, concomitant medications, and any ongoing signs or symptoms from the prior PCI-32765 protocol must be recorded in the site's source documentation.

Adverse Events

At all visits (except Post-treatment and Post-PD follow up assessments)

The accepted regulatory definition for an AE is provided in Section 7.1. Adverse events that meet the criteria for SAEs, events of special interest (Section 7.2.4), and AEs of grade 3 or higher in severity will be recorded from the subject's first dose of study drug until 30 days after study drug discontinuation or start of a new anticancer therapy. Important additional requirements for reporting SAEs are explained in Section 7.2.

Concomitant Medication Use

At screening visit and during study when associated with protocol specified AE or SAE. Verify concomitant medication use to ensure subjects' eligibility to remain on study and when associated with a protocol specified AE/SAE. See Section 7.0 for further AE/SAE details.

Confirmation of Eligibility

Screening

Perform all necessary procedures and evaluations to document that the subject meets each eligibility criterion. Screening evaluations must be completed within 14 days before the subject's first dose of PCI-32765 under this protocol.

Physical Examination and Vital Signs

At all visits (except Post treatment and Post PD follow up assessments)

The screening physical examination will include, at a minimum, the general appearance of the subject, height (screening only) and weight, and examination of the skin, eyes, ears, nose, throat, lungs, heart, abdomen, extremities, musculoskeletal system, nervous system, and lymphatic system.

Symptom-directed physical exams will be done during the treatment period and at the Safety Follow-up Visit.

Vital signs will include blood pressure, pulse, respiratory rate, and body temperature. Vital signs and weight will be measured at every visit. Screening vital signs and weight do not need to be repeated if performed on prior PCI-32765 protocol within 14 days before the first administration of study drug on this protocol.

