Disease assessments, as outlined by histology-specific guidelines, should be performed every 3 cycles (±7 days) while on study treatment. Disease assessments will include physical examination, disease-related symptoms, CBC, radiologic exam by computed tomography (CT) scan or positron emission tomography (PET), and/or bone marrow biopsy (refer to Section 6.2 for response assessment guidelines). Data from bone marrow examinations, including analysis for minimal residual disease (MRD) (bone marrow or peripheral blood if bone marrow is unavailable or considered inappropriate), will be collected and should be performed if subject meets all other criteria for CR.

Study Drug Accountability

At all visits (except Follow-up Phase)

Refer to Section 9.8.

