6.3.2 Post-treatment Phase

The Post-treatment Phase will extend from the discontinuation of treatment up until the subject has progressive disease or other criteria listed in Section 4.3. Subjects will be followed approximately every 3 months (±7 days) for disease progression and initiation of any subsequent anticancer therapy.

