6.3.3 Post-disease Progression Phase

After disease progression, follow subject for survival status (including cause of death) by clinic visit or phone contact, as well as collection of subsequent anticancer therapy once every 3 months (± 7 days) until the end of study.

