7.2.2 Assessment of Adverse Events

Investigators will assess the occurrence of AEs and SAEs at all subject evaluation time points during the study. All AEs and SAEs whether volunteered by the subject, discovered by study personnel during questioning, or detected through physical examination, clinically significant laboratory test, or other means will be recorded in the subject's medical record and on the AE eCRF and, when applicable, on a SAE Worksheet.

Each recorded AE or SAE will be described by its duration (i.e., start and end dates), severity, regulatory seriousness criteria, if applicable, suspected relationship to the investigational product (see following guidance), and any actions taken.

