7.2.6 Other Malignancies

In addition to all routine AE reporting, all new malignant tumors including solid tumors, skin malignancies and hematologic malignancies are to be reported for the duration of study treatment and during any protocol-specified follow-up periods including post-progression follow-up for overall survival.

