Appendix 3. Schedule of Assessments

	Screeninga	Treatment Phase	Follow-up Phase		
		Safety and Efficacy Every 3 Cycles (84 days) ±7 days	Safety Follow-up Prior to anticancer tx or 30 (±7) days after last dose	Post-treatment Follow-up every 3 cycles (84 days) ±7 days until PD ^b	Post-PD Follow-up every 3 months (±7 days)
Informed consent	X				
Confirm eligibility	X				
Medical history	X				
PE ^c /Vital signs ^d /Weight ^d	X	X	X		
Eye-related symptoms	X	X	X		
ECOG status		X	X		
Lab assessments:					
Urine pregnancy test ^e	X		X		
Hematology ^t	X	X	X		
Serum chemistry ^g	X	X	X		
Pharmacodynamics & Pharmacokinetics ¹		Will only be collected when a subject progresses			
Predictive biomarkers & mechanisms of resistance		Approximately once per year			
ECG		If clinically ir	dicated (eg, subjects with palpitations,	lightheadedness)	
Dispense study drug ^h		X			
Study drug compliance		X			
Disease assessment ¹		X		X	
Concomitant medications ^j	X	X	X		
New anti-cancer treatment ^m	•		X	X	X
Adverse events ^k	X	X	X		
Survival			_		X

- a. Screening tests should be performed within 14 days before the first administration of study drug, unless otherwise indicated.
- b. Subjects who did not progress on treatment, but discontinued study drug will be followed every 3 cycles for disease progression.
- c. The screening PE will include, at a minimum, the general appearance of the subject, height (screening only) and weight, and examination of the skin, eyes, ears, nose, throat, lungs, heart, abdomen, extremities, musculoskeletal system, nervous system, and lymphatic system. Symptom-directed physical examinations will be performed thereafter.
- d. Vital signs (blood pressure, pulse, respiratory rate, and temperature) will be assessed. Screening vital signs and weight do not need to be repeated if performed during a prior PCI-32765 protocol within 14 days before the first administration of study drug during the current protocol.
- e. Women of childbearing potential only. If positive, pregnancy must be ruled out by ultrasound to be eligible.

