- f. Hematology includes complete blood count with differential and platelet count. Screening hematology does not need to be repeated if performed on prior PCI-32765 protocol within 14 days before the first administration of study drug on this protocol. Subjects who roll into PCYC-1103-CA Study with < 12 months of study drug exposure will need to have hematology performed every 30 days (±7 days) till completion of 12 months on study drug and then hematology will be extended to every 3 cycles (±7 days) while on study treatment.
- g. Serum chemistry includes glucose, calcium, albumin, total protein, sodium, potassium, CO₂, chloride, blood urea nitrogen (BUN), creatinine, alkaline phosphatase, ALT, AST, and total bilirubin. Screening chemistry does not need to be repeated if performed on prior PCI-32765 protocol within 14 days before the first administration of study drug on this protocol. Serum chemistry will be performed every 3 cycles while on study treatment.
- h. One cycle is once daily administration for 28 days. Dispense sufficient study drug until the next scheduled visit.
- i. Objective response will be categorized as complete response (CR), partial response (PR), stable disease, or progressive disease based on the guidelines of each histology (refer to Appendix 4, Appendix 5 and Appendix 6. The response assessments will be performed once every 3 cycles during the Treatment Phase. All responses must be maintained for at least 2 months to be considered confirmed. Complete responses (CRs) must be confirmed by bone marrow biopsy/aspirate. Progressive disease (PD) must be confirmed by CT. To facilitate lymph node, liver, and spleen assessments in subjects, obtain a CT scan of the chest, abdomen, and pelvis, every 3 cycles for the first 18 cycles from the subject's first dose of study drug in the parent study, then every 6 cycles up to cycle 36, then every 12 cycles (annually) thereafter.
- 1. Verify concomitant medication use to ensure subjects' eligibility to remain on study. Record concomitant medications at screening visit and when associated with protocol specified AEs and with SAEs.
- k. Grade 3 and 4 AEs as well as all SAEs, exceptions (refer to Section 7.1.1) and events of special interest to be collected (refer to Section 7.2.4
- 1. Pharmacodynamic and Pharmacokinetic samples to be collected at the visit when it is determined that the subject has PD.

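### New malignancies must be reported through post-progression follow-up, but no scheduled follow-up contact asks about them; Sections 6.1 and 7.2.1 also end adverse event recording on different rules

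*Protocol*

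**What the plan says.** **Malignancies.** Section 7.2.6 sets a duty on top of routine AE reporting. All new malignant tumours, skin cancers included, are to be reported on treatment and "during any protocol-specified follow-up periods including post-progression follow-up for overall survival". Section 7.1.1 also lists other malignancies among the events collected whatever their grade.

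**Where AEs are assessed.** Section 7.2.2 is general: "Investigators will assess the occurrence of AEs and SAEs at all subject evaluation time points during the study". Section 6.1 (Adverse Events) is narrower: "At all visits (except Post-treatment and Post-PD follow up assessments". In Appendix 3 the AE row is marked for Screening, Treatment and Safety Follow-up only. Its footnote k reads "Grade 3 and 4 AEs as well as all SAEs, exceptions (refer to Section 7.1.1) and events of special interest to be collected".

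**What the later contacts contain.** Section 6.3.2 follows Post-treatment subjects "for disease progression and initiation of any subsequent anticancer therapy". After progression, Section 6.3.3 asks sites to "follow subject for survival status (including cause of death) by clinic visit or phone contact, as well as collection of subsequent anticancer therapy".

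**End of AE recording.** Section 6.1 gives two end points joined by a bare *or*: 30 days after discontinuation, and the start of new anticancer therapy. Section 7.2.1 gives one: 30 days after the last dose. After that, it asks only for serious events judged related to study drug.

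**The concern.** The purpose of this extension study is long-term safety, and Section 1.4.3.4 names other malignancies as a risk of the drug. Such events can appear late, after a subject has stopped treatment. A site that organises its follow-up contacts from Section 6.1 and Appendix 3 would have no item telling it to ask about them once the Safety Follow-up Visit is over. Events that are not collected cannot be recovered in the analysis.

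The end-date question is separate. The primary endpoint is the frequency, severity and relatedness of AEs. If two sections close the recording window differently, two sites can record different events for the same clinical course, both of them following the protocol.

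**Working it through.** No figure in the protocol needs reproducing here. The check sets the sections side by side and adds two small calculations.

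**1. Does any scheduled item reach malignancies after Safety Follow-up?**

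| Source | Post-treatment phase | Post-PD phase |
|---|---|---|
| 7.2.6 | report new malignancies | report new malignancies |
| 6.1, Adverse Events | excluded | excluded |
| Appendix 3, AE row (footnote k) | not marked | not marked |
| Appendix 3, items marked X | disease assessment; new anti-cancer treatment | new anti-cancer treatment; survival |
| 6.3.2 / 6.3.3 | progression; subsequent therapy | survival and cause of death; subsequent therapy |
| Malignancy items | 0 | 0 |

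The only schedule row that reaches malignancies is the AE row, because footnote k points to the exceptions in 7.1.1. That row ends at Safety Follow-up. The table was read from a PDF, but its marks agree with the text of 6.1, 6.3.2 and 6.3.3, so the gap is not a reading error.

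Section 6.1 is also narrower in content than 7.1.1. It lists serious events, events of special interest and events of Grade 3 or higher. The only event of special interest defined under 7.2.4 is major hemorrhage. A non-serious, low-grade skin cancer is therefore missing from the 6.1 list even during treatment; 7.1.1 and 7.2.6 are what bring it in.

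**2. How many contacts are involved?**

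- Post-treatment: 3 cycles × 28 days = 84 days; 365 / 84 = 4.3 a year.
- Post-PD: every 3 months; 12 / 3 = 4 a year.

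**3. Do other items fill the gap?** In part.

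- Post-treatment disease assessment: "Disease assessments will include physical examination, disease-related symptoms, CBC, radiologic exam by computed tomography (CT) scan", among other tests. It may reveal a second tumour, but it is aimed at the lymphoma or CLL.
- The "New anti-cancer treatment" row, in both phases, would pick up a second cancer given systemic therapy. A skin cancer that is simply excised need not appear there.
- Cause of death, after progression, finds fatal cases only. These contacts may be by telephone, and no physical examination is scheduled.
- Section 7.2.1, after day 30, covers serious events judged related.

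A locally treated, non-serious skin cancer can pass through all four. Section 1.4.3.4 gives non-melanoma skin cancer as the most frequent second malignancy (4 to 11%, against 5 to 14% for all other malignancies). These ranges describe patients treated with the drug and are not rates for the follow-up period. They show that the risk is not rare and that its commonest form is the one most easily missed.

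**4. How far apart are the AE end dates?** Let new therapy start on day d after the last dose, with d below 30. If the *or* in 6.1 means the earlier date, 6.1 closes on day d and 7.2.1 on day 30:

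disputed days = 30 − d

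| d | 1 | 7 | 14 | 21 | 29 |
|---|---|---|---|---|---|
| Disputed days | 29 | 23 | 16 | 9 | 1 |

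The values of d are illustrative, not trial data. If 6.1 instead means 30 days after new therapy starts, its window runs past that of 7.2.1. The sections differ on both readings. The rule that the earlier date governs is stated in 6.3.1 for the timing of the Safety Follow-up Visit, not for the AE window. Because that visit is brought forward ahead of new therapy, no AE visit is scheduled for the disputed days.

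**The case against.** The strongest reply is that 7.2.6 is binding in its own right. It is written as an addition to routine AE reporting and names the follow-up periods, while the 6.1 exclusion sits under the routine AE heading. A site can obey both. On this view only a table row is missing, and other duties after day 30, such as related serious events, have no row either. The eCRFs and their completion guidelines may well prompt for malignancies. Much of this stands: the requirement exists, the forms are not shown, and the finding is limited to the protocol text. But 7.2.6 asks for active reporting over a long period, and the parts of the protocol that tell sites what to do at each contact do not carry it.

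A second reply is that 7.2.2 refers to evaluations within the reporting period of 7.2.1. That is a possible intention. As written, though, it covers all evaluation time points during the study, and Post-treatment visits with a physical examination are such time points. The conflict with 6.1 is real in the wording.

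A third reply is that the end-date conflict is small. That is fair. It concerns only subjects who start new therapy within 30 days of the last dose, and mainly non-serious Grade 3 or 4 events, because 7.2.1 separately covers deaths within 30 days and later related serious events. The study also tests no hypothesis. Both points concern data collection rather than choice of analysis.

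**Conclusion.** The concern holds on both points, as inconsistencies that should be fixed.

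**Malignancies.** The protocol requires reporting throughout follow-up but schedules no malignancy item at any Post-treatment or Post-PD contact. Under-ascertainment is plausible, chiefly of locally treated skin cancers. Its size cannot be derived from the protocol, and it depends on what the eCRFs ask. Most of these events fall outside the 30-day AE window, so the loss would be to the malignancy record under 7.2.6 more than to the primary-endpoint counts.

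**AE end date.** Sections 6.1 and 7.2.1 disagree by 30 − d days for a subject starting new therapy on day d, if 6.1 means the earlier date. This does touch the primary endpoint. The share of subjects affected is not given.

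That the wording conflicts is certain. The effect on the data is a reasoned expectation and has not been measured.

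**What to change.** 1. **Malignancies.** Add a new-malignancy item to the Post-treatment and Post-PD columns of Appendix 3 and to Sections 6.3.2 and 6.3.3. State in 6.1 that this item is exempt from the exclusion of those contacts. Align 7.2.2 with 6.1 on which contacts assess AEs. The cost is some wording, one schedule item and one question at contacts that already take place about every three months.
2. **AE end date.** State one end date in both 6.1 and 7.2.1. If new anticancer therapy can end recording, say explicitly whether the earlier or the later date governs. Bring the illustrative bullet in 7.1.1 into line. The cost is wording only.

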6.2 INVESTIGATOR'S ASSESSMENT OF RESPONSE TO TREATMENT

The investigator must evaluate the subject's response to treatment based on Guidelines for the Diagnosis and Treatment of CLL⁹ (Appendix 4), International Working Group Revised Response Criteria for Malignant Lymphoma ¹⁰ (Appendix 5), and Waldenström's Macroglobulinemia (WM)¹¹ (Appendix 6).

6.2.1 Baseline Tumor Assessment

As this is a long-term extension study, the baseline tumor assessments are derived from the baseline tumor assessment from the prior PCI-32765 protocol.

The exception is those subjects from PCYC-04753 who had disease progression and enrolled in this study to receive higher dose level. Their baseline tumor assessment must be done within 30 days of starting on this protocol.

6.2.2 Assessment of Response to Treatment

Objective response will be categorized as complete response (CR), complete response with incomplete marrow recovery (CRi), nodular partial response (nPR), partial response (PR), partial response with lymphocytosis (PRL), stable disease (SD), or progressive disease (PD) based on the guidelines of each histology (refer to Appendix 4, Appendix 5, and Appendix 6). The response assessments will be performed once every 3 cycles (±7 days) during the Treatment Phase. All responses must be maintained for at least 2 months to be considered confirmed. To facilitate lymph node, liver, and spleen assessments in subjects, obtain a CT scan of the chest,

abdomen, and pelvis, every 3 cycles for the first 18 cycles from the subject's first dose of study drug in the parent study, then every 6 cycles up to cycle 36, then every 12 cycles (annually) thereafter.

- Progressive Disease (PDs) must be confirmed by CT scan.
- Complete responses (CRs) must be confirmed by bone marrow biopsy/aspirate. For subjects who obtain complete response (CR), subsequent scans are only required to confirm disease progression.

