Study design:	This is an open-label, monotherapy, multicenter, extension study open to subjects meeting requirements for roll over from their parent protocol and want to continue receiving study drug. Subjects from PCYC-04753 who had disease progression may enroll in this study at a higher dose level of PCI-32765 (not to exceed 840 mg/day) than dose level in PCYC-04753 study. Subjects enrolled in this study will receive once daily dosing with PCI-32765 at the same dose level they were receiving in the parent study. One cycle is 28 days. Treatment may be continued as long as there is no evidence of progressive disease or unacceptable toxicity. Safety and efficacy assessments will be performed at a minimum of every 3 cycles. At each visit, adverse events (AEs) of Grade 3 or 4 in severity, which are either new or represent detectable exacerbations of pre-existing conditions, events of special interest and ongoing AEs from parent protocol will be recorded. All serious adverse events (SAEs) must be recorded. Efficacy assessments will be performed in accordance with the Guidelines for the Diagnosis and Treatment of CLL ⁹ (Appendix 4), International Working Group Revised Response Criteria for Malignant Lymphoma ¹⁰ (Appendix 5), and Waldenström's Macroglobulinemia (WM) ¹¹ (Appendix 6). If signs and symptoms provide evidence of progressive disease (PD), PD must be confirmed by CT. Upon discontinuation of study treatment, a Safety Follow-up Visit (SFU) will be performed prior to the start of a new anticancer		
	therapy or approximately 30 (± 7) days after the last dose of study drug, whichever occurs first. If a subject discontinues treatment for reasons other than disease progression, response assessments will be continued approximately every 3 cycles until disease progression.		
	Once a subject has progressive disease, collect subsequent anticancer therapy and subject survival status approximately once every 3 months. At a visit when it is determined that a subject has		

	progressed, collect blood samples for pharmacodynamics and pharmacokinetics analyses (e.g., Btk occupancy and B cell activation) (refer to Section 6.1.)		
Major inclusion/exclusion criteria:	For the complete list of inclusion/exclusion criteria refer to Section 4.0.		
	Major Inclusion Criteria:		

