Appendix 5. Response Assessment Criteria for Lymphoma (Cheson 2007)¹⁰

Response	Definition	Nodal Masses	Spleen, Liver	Bone Marrow
CR	Disappearance of all evidence of disease	(a) FDG-avid or PET positive prior to therapy; mass of any size permitted if PET negative (b) Variably FDG-avid or PET negative; regression to normal size on CT	Not palpable, nodules disappeared	If infiltrate present at screening, infiltrate cleared on repeat biopsy; if indeterminate by morphology, immuno- histochemistry should be negative
PR	Regression of measurable disease and no new sites	≥ 50% decrease in SPD of up to 6 largest dominant masses; no increase in size of other nodes (a) FDG-avid or PET positive prior to therapy; ≥1 PET positive at previously involved site (b) Variably FDG-avid or PET negative; regression on CT	≥ 50% decrease in SPD of nodules (for single nodule in greatest transverse diameter); no increase in size of liver or spleen	Irrelevant if positive prior to therapy; cell type should be specified
SD	Failure to attain CR/PR or progressive disease	(a) FDG-avid or PET positive prior to therapy; PET positive at prior sites of disease, and no new sites on CT or PET (b) Variably FDG avid or PET negative; no change in size of previous lesions on CT		

Abbreviations: CR = complete response, CT = computed tomography, FDG = [¹⁸F]fluorodeoxyglucose, PET = positron-emission tomography, PR = partial remission, SD = stable disease, SPD = sum of the product of the diameters

Progressive disease for Non-Hodgkin's lymphoma is characterized by any new lesion or increase by $\geq 50\%$ of previously involved sites from nadir for example:

- Appearance of a new lesion(s) > 1.5 cm in any axis, $\ge 50\%$ increase in SPD of > 1 node, or $\ge 50\%$ increase in longest diameter of a previously identified node >1 cm in short axis
- Lesions PET positive if FDG-avid lymphoma or PET positive before therapy
- > 50% increase from nadir in the SPD of any previous lesions in the liver or spleen
- New or recurrent involvement in the bone marrow

An increase of \geq 50% in blood lymphocytes with \geq 5 x 10⁹/L B cells only in setting of enlarging lymph node, liver, or spleen (note: isolated elevation of WBC by itself will not be considered progressive disease unless subject becomes symptomatic from this)

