Appendix 6. Response Assessment Criteria for Waldenström's Macroglobulinemia (Kimby 2006)¹¹

Response	Definition
CR	A disappearance of serum and urine monoclonal protein determined by immunofixation, absence of malignant cells in bone marrow determined by histologic evaluation, resolution of adenopathy/organomegaly, (confirmed by computed tomography [CT] scan), and no signs or symptoms attributable to WM. Recommendation of the CR status is required ≥ 6 weeks later with a second immunofixation.
PR	$A \ge 50\%$ reduction of serum monoclonal IgM concentration determined by protein electrophoresis, $\ge 50\%$ decrease in adenopathy/organomegaly on physical examination or on CT scan, and no new symptoms or signs of other active disease.
SD	A < 25% reduction and < 25% increase of serum monoclonal IgM determined by electrophoresis without progression of adenopathy/organomegaly, cytopenias, or clinically significant symptoms caused by disease and/or signs of WM.
PD	$A \ge 25\%$ increase in serum monoclonal IgM by protein electrophoresis confirmed by a second measurement or progression of clinical significant findings caused by disease (eg, anemia, thrombocytopenia, leukopenia, or bulky adenopathy/organomegaly) or symptoms (eg, unexplained recurrent fever $\ge 38.4^{\circ}$ C, drenching night sweats, $\ge 10\%$ weight loss, hyperviscosity, neuropathy, or symptomatic cryoglobulinemia) attributable to WM.

Abbreviations: WM=Waldenström's Macroglobulinemia, CR = complete response, CT = computed tomography, PR = partial response, SD = stable disease, PD=progressive disease

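### Every PD must be confirmed by CT, but the WM and lymphoma criteria include progression that CT cannot show; the WM criteria also leave an IgM reduction of 25% to <50% without a category

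*Protocol*

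**What the plan says.** The CT rule appears in three places in the protocol.

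- Section 6.2.2: "Progressive Disease (PDs) must be confirmed by CT scan".
- Appendix 3, footnote i: "Progressive disease (PD) must be confirmed by CT".
- Synopsis, study design: "If signs and symptoms provide evidence of progressive disease (PD), PD must be confirmed by CT".

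None of these limits the rule to a histology or to a type of progression. Section 6.2.2 also says that response, including PD, is categorized "based on the guidelines of each histology", pointing to Appendices 4 to 6. Section 4.3 uses the same appendices for stopping treatment.

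For WM, the PD row of Appendix 6 requires a rise of at least 25%, described as "increase in serum monoclonal IgM by protein electrophoresis confirmed by a second measurement or progression of clinical significant findings caused by disease"; symptoms attributable to WM are a further alternative. The SD row requires a reduction under 25% and an under-25% "increase of serum monoclonal IgM determined by electrophoresis without progression of adenopathy/organomegaly, cytopenias, or clinically significant symptoms caused by disease". The PR row requires at least a 50% "reduction of serum monoclonal IgM concentration determined by protein electrophoresis", together with nodal or organ shrinkage and no new symptoms or signs. For lymphoma, Appendix 5 lists "New or recurrent involvement in the bone marrow" among its examples of PD.

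**The concern.** Two separate faults affect how an investigator classifies a subject at a visit.

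First, the confirmation rule and the definitions of PD do not fit together. A site that applies the CT rule strictly will not record PD for a WM subject with twice-measured IgM progression and an unchanged scan. A site that applies Appendix 6 will. The listing of PD and death events (Sections 3.3 and 8.0) could then differ between sites for the same clinical course. PD status also has operational effects: it governs how long treatment continues (Section 3.1), triggers the pharmacokinetic and pharmacodynamic samples (Section 6.1), and moves the subject from post-treatment to post-progression follow-up (Sections 6.3.2 and 6.3.3).

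Second, the WM categories are not exhaustive. A subject whose IgM has fallen by 25% to <50% has no defined entry for the documented-responses endpoint.

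**Working it through.** The protocol states no figure on this point, so there is none to reproduce. The check compares the CT rule with each PD criterion and then tests whether the WM IgM thresholds cover every value.

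**Step 1: which PD criteria can a CT of chest, abdomen and pelvis confirm?**

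| Criterion | Source | Confirmation named there | CT can confirm? |
|---|---|---|---|
| New lesions or growth of nodes, liver or spleen | Appendices 4, 5 | none | yes |
| Bulky nodes or organ enlargement in WM | Appendix 6 | none | yes |
| IgM rise of at least 25% in WM | Appendix 6 | second IgM measurement | no |
| Anemia, thrombocytopenia or leukopenia due to WM | Appendix 6 | none | no |
| Symptoms due to WM, such as hyperviscosity or neuropathy | Appendix 6 | none | no |
| Marrow involvement in lymphoma | Appendix 5 | none | no |

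A narrower case of the same kind is the symptomatic white-cell rise that Appendices 4 and 5 allow to count as PD.

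**Step 2: is there a fallback category?** Appendices 4 and 5 define SD as the remainder once CR, PR and PD are not met. Appendix 6 does not. Its SD row needs an IgM increase under 25% and no progression of cytopenias or clinically significant symptoms. A WM subject progressing by IgM, cytopenia or symptoms alone is therefore neither CT-confirmed PD nor SD.

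**Step 3: do the WM IgM thresholds cover every value?** Let R be the reference IgM and r = 100 × (IgM − R)/R. Take the non-IgM components as compatible with each category, and CR as not met.

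- PR: r ≤ −50
- SD: −25 < r < +25
- PD: r ≥ +25
- No category: −50 < r ≤ −25, that is 0.50R < IgM ≤ 0.75R

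A scan of r from −100 to +100 in steps of 0.1 gives PR up to −50.0, nothing from −49.9 to −25.0, SD from −24.9 to +24.9, and PD from +25.0. There is one gap and no overlap. The category list in Section 6.2.2 contains no minor response that would fill it.

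**Step 4: illustration.** The protocol gives no IgM values, so R is assumed.

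- R = 40 g/L: PR at or below 0.50 × 40 = 20; no category above 20 and up to 0.75 × 40 = 30; SD above 30 and below 1.25 × 40 = 50; PD at 50 or above.
- A subject at 25 g/L has r = 100 × (25 − 40)/40 = −37.5% and, without progression, no category.
- A subject at 50 g/L or more on two measurements with an unchanged CT is PD by Appendix 6, unconfirmed under Section 6.2.2, and not SD.
- R = 20 g/L: the uncovered band is above 10 and up to 15 g/L.
- R = 60 g/L: the uncovered band is above 30 and up to 45 g/L.

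**The case against.** The strongest counter-reading is that the CT sentence in Section 6.2.2 is an imaging instruction. It follows a sentence on scanning to assess nodes, liver and spleen, and the next bullet also concerns scans. Sections 4.3, 6.2 and 6.2.2 separately make the histology guidelines govern PD. This reading is possible for that bullet alone. It does not survive the synopsis, which applies CT confirmation where the evidence is signs and symptoms, or footnote i, which states no limit.

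Several narrower points stand and limit the size of the problem.

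- No routine marrow surveillance is scheduled, so marrow-only progression would come to light only on an unscheduled biopsy.
- A WM subject in the IgM gap plainly does not meet PR. No response is gained or lost; only the label for a non-responder is undefined.
- Appendix 6 names no reference value for the 25% rise. If nadir were meant, as Appendix 5 uses, the PD cut-point in the illustration would move: from a nadir of 25 g/L it is 1.25 × 25 = 31.25 g/L, not 50. The gap remains for any subject whose lowest value to date lies in the band, because such a subject has no rise from nadir.
- PD and response are non-primary and only listed, and Section 4.3 allows treatment to stop for histology-defined PD or by investigator decision. No subject has to stay on failing therapy because of this wording.

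**Conclusion.** Both faults hold on the text. The CT rule contradicts the WM criteria for progression by IgM, cytopenia or symptoms, and the lymphoma criterion for marrow involvement. Progression by nodal or organ growth is unaffected. The WM table leaves exactly one IgM band, a reduction of 25% to <50%, without a category. The band is exact from the printed thresholds for change from baseline; the g/L values depend on the assumed baseline, and the illustrative PD and SD limits also depend on using that baseline as the reference for a rise.

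The number of subjects affected cannot be stated from the protocol. The primary endpoint, adverse events, is untouched and no hypothesis is tested. What is at risk is the consistency of the PD and response listings, of sampling at progression, and of the switch of follow-up phase. The wording should be corrected, but the point does not threaten the study's main purpose.

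**What to change.** In the synopsis, Section 6.2.2 and Appendix 3 footnote i, require CT confirmation for nodal or organ progression only. For other progression, require the evidence that fits the criterion in Appendices 4 to 6:

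- a second IgM measurement for serological progression in WM;
- marrow examination for marrow progression;
- documented clinical or laboratory findings for progression by cytopenia or symptoms.

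Separately, redefine WM SD in Appendix 6 as not meeting CR, PR or PD, in line with Appendices 4 and 5. A minor-response category for an IgM reduction of 25% to <50% would also close the gap, but it would have to be added to the category lists in Section 6.2.2 and footnote i as well. The residual definition is simpler.

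The cost is wording in three places and one row of Appendix 6. No new procedure is introduced: Appendix 6 already calls for the second IgM measurement, and marrow progression is found by marrow examination. IgM and protein electrophoresis are not named in the chemistry list or the disease-assessment description in Section 6.1, so the current WM criteria already rely on a test that the schedule only implies.
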